Health care worker (provider) survey	-Demographics, cadre, technology literacy, knowledge, attitudes, practices, aptitudes, past training, time spent on ACT activities	All enrolled health care workers (N=33 clusters x ~2+ HCWs/cluster=66+)	PRE Q.1 Q.4	Provider survey (SurveyCTO)
Focus group discussions (FGDs)/In depth interviews (IDIs)	-Learn about HCW feasibility and acceptability Compare SOC to ENH and PRE/Q1/Q4	Health care workers (N=8 groups x 3 times~=24 FGDs) (N=3 IDIs x 8 facilities x 3 times~=72 IDIs)	PRE Q.1 Q.4	Semi-structured guides (audio recording) (Survey CTO to document participants and timing)
Fidelity Assessments (FA)	-Observe HCW conducting true index and/or contact encounters	Health care workers, indexes, contacts ((N= 33 cluster x minimum of 2 indexes/cluster=66-600) (N= 33 cluster x minimum of 2 contacts/cluster=66-200)	Q.1-4	Fidelity assessment tool (audio recording to paper to SurveyCTO)
Index exit interviews Contact exit interviews (Xls)	-Examine index acceptability -Examine contact acceptability	Indexes and contacts: (N= 33 cluster x minimum of 2 indexes/cluster=66-600) (N= 33 cluster x minimum of 2 contacts/cluster=66-200)	Q.1-4	Index exit interview (SurveyCTO)
Time and motion assessment (TM)	-Assess the effort to which HCWs work on each activity	Health care workers N=(~2-3/cluster x 33 facilities=66-100 days of observation)	Q.1-4	Time and motion survey (paper to SurveyCTO)
Effectiveness outcomes (EF)				
Total potential indexes	#ART patients who were supposed to be assessed per quarter plus the #new HIV+ patients per quarter	N=33 clusters x 8 quarters=264	Q.1-8	ART and HTS registers HTS registers (register to SurveyCTO)
# indexes, #contacts elicited, # STKs distributed	Number of indexes captured, contacts elicited and STKs distributed	N=33 clusters x 8 quarters=264	Q.1-8	Index and contact registers
# contacts tested # HIV+ contacts	Number of contacts returned and the proportion HIV+	N=33 clusters x 8 quarters=264	Q.1-8	Index and contact registers

Evaluation framework

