At each of the 33 clusters, at least 2 ACT encounters between health workers and indexes at least 2 ACT encounters between health workers and contacts will be audio-recorded. A minimum of 132 observations total are needed for both indexes and contacts (4/per cluster), but up to 200 contact encounters and 600 index encounters may be conducted. For indexes, attempts will be made to achieve balance between recruitment from the ART and HTS settings. For contacts, attempts will be made to achieve balance between the clinic and community settings.

Each audio-recording will be scored by two research officers blinded to the study arm and the two scores will be averaged. This tool has been field-tested.

Analyses: Generalized estimating equations (GEE) to account for potential correlation at the cluster level will be implemented to compare health worker fidelity scores between the enhanced and standard arms. Models with identity links and normal distributions will be used to compare means between the two arms. A working correlation structure will account for the correlated nature of observations from the same cluster. Models will contain a term for randomization arm. To assess fidelity maintenance over time, we will implement models with an interaction

term between time and randomization arm. To assess differences by setting (indexes: ART vs. HTS; contacts: clinic vs. community), we will implement an interaction term between randomization arm and setting. Indexes and contacts will be analyzed separately. Data from the authentic and simulated fidelity assessments (below) may be combined.

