Statistical power and sample size: Sample size calculations are based on data collected during our pilot assessment of provider fidelity. The pilot fidelity score standard deviation, after rescaling to percentage points, was 20.5%. With 132 fidelity assessments from 33 clusters and assuming SD=20.5% and a working correlation estimate of 0.3 or smaller, we will have >99% statistical power to detect a 30 percentage point difference between means (90 versus 60) between the enhanced and standard arms. Even with smaller differences between arms of 15 percentage points (75 versus 60), we have >81% statistical power to detect a difference. Although only 132 authentic fidelity assessments are needed to achieve >80% power, up to 200 authentic fidelity assessments (contact clients) and 600 (index clients) per cluster may be collected to examine trends within sub-groups. Power was calculated by inverting the closed-form sample size equation from section 4.1 of Liu & Liang (1997), where the average cluster size was used in place of n for a reasonable power approximation.

Additional (tertiary/exploratory) implementation outcomes: Exploratory implementation outcomes of interest include simulated fidelity assessments, facility adoption of and adherence to the implementation strategies, health worker feasibility and acceptability, and patient acceptability.

- **Health care worker knowledge, attitudes, practices:** These constructs will be assessed through the health worker survey.
- **Simulated fidelity assessments:** These will be analyzed similarly to the authentic fidelity assessments described above. However, rather than conducting these with real patients and contacts, they will be conducted with actors simulating indexes and contacts. Each enrolled health care workers may participate in staged fidelity assessments with indexes and contacts.

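### The >81% power for a 15-point fidelity difference needs all 132 encounters in one model; each separate index or contact analysis is guaranteed only 66, which gives 69% to 80%

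*Combined protocol and SAP*

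**What the plan says.** All references are to the Combined protocol and SAP, mainly the section Aim 1 Analytic methods and power calculations.

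- **Minimum sample.** The paragraph on the primary outcome requires at least 2 recorded index encounters and at least 2 recorded contact encounters per cluster: "A minimum of 132 observations total are needed for both indexes and contacts (4/per cluster"). The Data elements table, row Fidelity Assessments, gives the two minima separately: "minimum of 2 indexes/cluster=66-600" and "minimum of 2 contacts/cluster=66-200".
- **Analysis.** The Analyses paragraph describes GEE models with a term for arm, then interaction models for time and setting. It then states: "Indexes and contacts will be analyzed separately".
- **Power.** The paragraph on statistical power and sample size starts from these inputs: "With 132 fidelity assessments from 33 clusters and assuming SD=20.5% and a working correlation estimate of 0.3 or smaller". It claims more than 99% power for 30 points (90 versus 60), and then: "Even with smaller differences between arms of 15 percentage points (75 versus 60), we have >81% statistical power to detect a difference".
- **Sufficiency.** The same paragraph adds: "Although only 132 authentic fidelity assessments are needed to achieve >80% power". It explains encounters beyond that number as a means of looking at trends within sub-groups.

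**The concern.** The sample size in the power statement is not the sample size of any analysis that the plan describes. The 132 is reached only by adding index and contact encounters together, whereas the fidelity comparison is to be run once on indexes and once on contacts. At the stated minimum each model has 66 observations, 2 per cluster. No power is given for a model of that size.

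Fidelity is the primary outcome of Aim 1, and the plan tells the team that 132 recordings in total are enough. A team that stopped there would accept up to a 31% chance of missing a true 15-point difference in each comparison (1 − 0.691), where the text implies less than 19% (1 − 0.81). A null result for contacts or for indexes could then be read as coming from an adequately powered comparison.

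**Working it through.** **Inputs from the documents**

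- SD 20.5 percentage points; correlation 0.3 or smaller; differences of 15 and 30 points (Statistical power and sample size).
- 33 clusters randomised 2:1, so 22 standard and 11 enhanced (Study design and outcomes).
- Encounters per cluster, m: 4 if the types are pooled (132/33), 2 for each type alone (66/33).

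**Assumptions**

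- Two-sided 5% level. The Aim 1 section states neither level nor sidedness; 0.05 is stated for Aim 2.
- The plan cites a published closed-form equation that it does not reproduce. The standard design-effect formula is used instead, and is checked first against the plan's own figures.

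**Formulas**

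Var(difference) = SD² × [1 + (m − 1)ρ]/m × (1/11 + 1/22)

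Power = Φ(difference/SE − 1.96)

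SD² = 420.25 and 1/11 + 1/22 = 0.13636.

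**Step 1: reproduce the plan's figure (m = 4, ρ = 0.3)**

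Var = 420.25 × 1.9/4 × 0.13636 = 27.22, so SE = 5.217. For 15 points, 15/5.217 = 2.875 and power = Φ(0.915) = 82.0%. For 30 points, power is 99.99%. Both agree with the plan's claims of more than 81% and more than 99%. A one-sided 5% test would give 89.1% for 15 points, a poorer match.

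**Step 2: the same formula for each separate analysis (m = 2), 15 points**

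| Correlation | SE | 15/SE | Power |
|---|---|---|---|
| 0.3 | 6.103 | 2.458 | 69.1% |
| 0.2 | 5.864 | 2.558 | 72.5% |
| 0.1 | 5.614 | 2.672 | 76.2% |
| 0 | 5.353 | 2.802 | 80.0% |

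More than 81% is not reached at any correlation from 0 to 0.3.

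**Step 3: what 66 encounters can detect with 80% power**

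Detectable difference = (1.960 + 0.8416) × SE = 2.8016 × SE. This is 17.1 points at ρ = 0.3 and 15.0 points at ρ = 0.

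**Step 4: encounters of each type needed for 15 points at ρ = 0.3**

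- 80% power: m = 3.50 per cluster, 33 × 3.496 = 115.4, so about 116.
- 81% power: m = 3.73 per cluster, 33 × 3.733 = 123.2, so about 124.
- 4 per cluster (132 of each type): 82.0%.
- Ceilings: 200 contacts (m = 6.06) give SE 4.880 and 86.7%; 600 indexes (m = 18.2) give SE 4.404 and 92.6%.

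**Step 5: the 30-point claim at m = 2, ρ = 0.3**

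30/6.103 = 4.916, so power is 99.8%. This claim stands.

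**Sensitivity**

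With a t reference distribution on 31 degrees of freedom (33 clusters − 2), power at 66 falls to 66.3% (ρ = 0.3) and 77.5% (ρ = 0). With a one-sided 5% test it would be 79.2% to 87.6%, but Step 1 shows that the one-sided test fits the stated figure less well.

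**The case against.** The arithmetic is not in dispute. The strongest counter-argument concerns which analysis is primary. The sentence on separate analysis comes straight after the setting interactions, where indexes and contacts have different settings and separate models are unavoidable, so it might govern only those models. The plan names one primary fidelity outcome and one primary hypothesis, and it counts 132 across both types. On that reading the primary comparison is pooled and more than 81% is correct. However, the sentence stands alone, is not limited to the interaction models, and is the only statement on how the two types are handled. What does stand is that the plan never says how two separate results would answer its single hypothesis.

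Three further points limit the weight of the concern without removing it.

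- **Fallback effect.** The 15-point difference is secondary to the 30-point design claim, which survives. By the same formula a 20-point difference has about 91% power at 66 and correlation 0.3 (20/6.103 = 3.277; Φ(1.317)).
- **Floor.** Sixty-six is a minimum, and 69% is the worst corner of the assumed range. At 3 encounters per type per cluster, power is 77% at correlation 0.3 and 83% at 0.2. But the ceilings are not commitments, and the plan presents the minimum as sufficient.
- **Simulated assessments.** The plan allows these to be combined with the authentic ones. If two workers per cluster each did both kinds of simulation, each type would have about 4 observations per cluster. This is optional, though: simulated assessments are classed as exploratory, and the claim of more than 80% power is tied to authentic assessments.

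**Conclusion.** The concern holds. The stated power of more than 81% for 15 points belongs to a single model with all 132 encounters, whereas the plan specifies separate index and contact analyses that are each guaranteed 66. For those, power is 69.1% at correlation 0.3 and at most 80.0% at correlation 0. The statement that 132 authentic assessments are enough for more than 80% power fails for the same reason.

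This rests on the separate-analysis sentence applying to the main arm comparison, on a two-sided 5% level, and on the design-effect formula standing in for the cited equation. It concerns the 15-point difference at the stated minimum and leaves the 30-point claim intact. It should be corrected, because it misstates the power for the primary Aim 1 outcome, but it does not undermine the design.

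**What to change.** In the paragraph on statistical power and sample size, do one of the following.

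1. **Restate the power per analysis at 66 encounters.** For 15 points, about 69% at correlation 0.3 and 80% at correlation 0; or, equivalently, 80% power for about 17 points at correlation 0.3. Keep more than 99% for 30 points. Remove the statement that 132 assessments in total suffice for more than 80%. This changes wording only; the price is a less favourable stated power.
2. **Raise the minimum to 4 encounters of each type per cluster.** This gives 82.0% in each analysis at correlation 0.3. It adds 66 index and 66 contact recordings, each scored by two officers, so 132 × 2 = 264 more scorings. It stays within the ceilings of 600 and 200. About 3.5 per cluster (116 of each type) would be enough for 80%.
3. **If a pooled primary comparison is intended, say so** in the Analyses paragraph and limit the separate analyses to secondary models. The 132 then stands for the pooled comparison, but the separate analyses still need their own power statement if conclusions will be drawn from them.

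Under options 1 and 2, also state how the index and contact results together decide the single primary hypothesis. In all cases, state the significance level and sidedness for Aim 1. As an editorial matter, delete the words per cluster after the figures of 200 and 600 in the same paragraph; elsewhere in the protocol these are study totals.

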Consistent with implementation science best practices,^{13, 37, 38} we have used an evaluation framework, RE-AIM, to guide analysis.^{93, 94} The five RE-AIM constructs—Reach, Effectiveness, Adoption, Implementation, and Maintenance—align with our research questions. Reach, persons receiving the intervention, will be measured by the rate of potential indexes who are offered ACT. Effectiveness, the ability of an intervention to impact outcomes, will be measured by a range of service uptake outcomes. In addition, positive and negative aspects of index and contact experiences will be measured through exit interviews. Adoption will be measured by the proportion of the enhanced implementation package completed per site. Implementation will be assessed through fidelity assessments, measuring how well health workers adhere to counseling protocols. Maintenance, the degree to which a program becomes part of routine organizational practice, will be examined through the consistency in the other outcomes (effectiveness and implementation) over time. In addition, we expect to explore how the five RE-AIM domains relate to one another (Figure 8).^{83, 84} We hypothesize that adoption of blended learning activities will lead to better implementation and reach which, in turn, will lead to greater ACT effectiveness, and ultimately maintenance (sustainability) over time.

Aim 1 Analytic methods and power calculations (implementation outcomes)

In Aim 1, we will compare the implementation outcomes of the enhanced and standard arms. The primary hypothesis is that fidelity to counseling procedures will be better in the enhanced arm than the standard arm.

Primary outcome of interest (fidelity): The primary implementation outcome of interest is health worker fidelity to ACT counseling procedures. This was selected as the primary implementation outcome because the enhanced training directly targets this outcome. Fidelity will be assessed using a 15-item scale assessing the quality, completeness, and adherence to ACT procedures with raw scores ranging from 0-30 (and recalculated as 0 to 100 percentage points).

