Outcomes of interest: Five ACT service uptake outcomes will be measured from index and contact registers on a quarterly basis. Each of these outcomes will be measured as a count per cluster per calendar quarter (three-month period). We will use facility-level data because the facility (i.e. cluster) is the primary unit of randomization. With 33 clusters under observation for four quarters, the facility-level dataset for the primary analyses will contain 132 observations (33 clusters * 4 quarters), 44 observations in the enhanced arm and 88 observations in the standard arm. The full two-year analyses will contain 264 observations (33 clusters * 8 quarters). The following measures will be calculated on a quarterly basis:

- **Total potential indexes:** This is the total number of ART and HTS patients that should be screened for and potentially offered ACT.
- **1: Indexes who participate in ACT:** The number of indexes in the index register.
- **2: Number of contacts elicited:** The number of contacts listed by the participating indexes. Are they put into the index register here?
- **3a: Number of self-test kits distributed:** The number of HIV self-test kits given to indexes for secondary distribution. Often, this is used as a method for testing contacts, rather than presenting to the clinic.
- **3b: Number of contacts tested:** The number of contacts with a recorded HIV test result. These tests are typically performed by a health care worker.
- **4: Number of contacts diagnosed HIV-positive:** The number of contacts in the contact register with an HIV-positive test result.

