Analyses: Data from quarters 1 through 4 (the cluster RCT design) will be analyzed using a negative binomial mixed-effects model accounting for quarterly repeated measures within each cluster. Models will use a log link, contain terms for randomization arm, and the natural-log transformed number of potential indexes will be incorporated as an offset term. Key baseline variables of interest, such as district, will be adjusted for. Rate ratios and 95% confidence intervals will be used to estimate the effect sizes and quantify the precision of effect estimates for the main analyses which will compare the enhanced versus standard arms for rates of each service uptake outcome per the total number of potential indexes (5 main endpoints denoted above). Secondary endpoints will take the same approach and use a negative binomial mixed effects model as well. Several secondary endpoints are proportion measures; for those endpoints effect size will be measured using a risk ratio and corresponding 95% confidence interval comparing the enhanced versus standard arms. To assess maintenance, interaction terms between quarters and randomization arm will be included to assess whether effects remain constant, intensify, or diminish over time during quarters 1 through 6.

Statistical power assumption, models, and estimates: Sample size calculations were guided by data from the 33 proposed clusters in the two districts from 2019-2020. In these two districts (Machinga and Balaka), Tingatthe supports 34 MOH facilities with implementation of the national HIV program and supervises approximately 150 community health workers and 100 HIV diagnostic assistants. Two nearby facilities in Balaka will be combined for analysis such that the 34 facilities are handled as 33 clusters.

Across these 33 clusters, 4600 persons are diagnosed with HIV each year and another 49,000 are already taking ART. From this, we estimated 35 new HIV-positive diagnoses per cluster per quarter and 372 ART patients per cluster per quarter or approximately 407 total potential indexes per facility per quarter. On average, of these 407 total potential indexes, there were approximately 86 indexes identified (0.21), 97 contacts elicited (0.24), 12 self-test kits distributed (0.03), 25 contacts tested (0.06), and 3 contacts diagnosed as HIV-positive (0.007). These values informed our assumptions for the standard arm.

Power for primary analyses:

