Standard power formulas were not equipped for this cluster RCT design due to contingencies in the count outcomes with differing cluster sizes, repeated measures and within-facility correlated data. Thus, for power calculations in Aim 2, we applied these parameters to a simulation study of these facilities in SAS v9.4.^{87, 88} The number of total potential indexes per facility per quarter was accounted for as a statistical offset term.⁸⁹ The number of total potential

indexes per facility per quarter was generated from a Poisson distribution with a cluster-specific mean. Count values per cluster per quarter for each of 5 outcomes were generated from a negative binomial distribution with the random intercept variance, over-dispersion parameter, and arm-specific rates specified using a generalized linear mixed effects model with a log link. The Poisson facility-specific means, random intercept variances negative binomial over-dispersion parameters, and mean values for the standard arm were estimated from background data. To compute power, the simulated study data were analyzed using a negative binomial mixed-effects model accounting for repeated measures within a cluster. Statistical power was computed using simulation studies of 10,000 cluster RCT datasets. Based on these assumptions, and a significance level $\alpha=0.05$, we have **80-85% statistical power to detect a difference between the arms for each of the outcomes of interest**.

		Assumed values for empirical power calculations:							Statistical Power	
TPI denominators		Endpoint Rates		Effect size	Expected counts		Nuisance parameters			
Key measures:		Enhanced	Standard	RR	Enhanced	Standard	RIV	Scale		
0. Total potential indexes		n/a	n/a	1	407	407			n/a	
1. Total indexes		0.3100	0.2113	1.47	126	86	0.0981	0.0854	85%	
2. Contacts Elicited		0.3700	0.2383	1.55	151	97	0.1268	0.1880	81%	
3a. Self-test kits distributed		0.0650	0.0295	2.20	26	12	0.0001	1.9077	82%	
3b. Contacts Tested		0.1247	0.0614	2.03	51	25	0.3340	0.2847	85%	
4. HIV+ Contacts Diagnosed		0.0155	0.0074	2.10	6	3	0.3334	0.3039	82%	

RR=rate ratio
RIV = random intercept variance; estimated variance of the random intercept for cluster j
Scale parameter for the negative binomial mixed-effects model summarizes over-dispersion
Standard arm counts calculated by averaging background data from Oct 2019-April 2020 and Sep–Nov 2020
Nominal type I error rate of $\alpha=0.05$ is used throughout, with no adjustment for multiple endpoints

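### Aim 2 maintenance rests on an arm-by-quarter interaction over quarters 1-6 with no margin, interval criterion or power, so it cannot show that effects held, and crossover in quarters 5-6 distorts it

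*Combined protocol and SAP*

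**What the plan says.** The Evaluation framework section makes maintenance one of the five RE-AIM constructs. It "will be examined through the consistency in the other outcomes (effectiveness and implementation) over time".

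For service uptake, the Analyses paragraph of the Aim 2 section says that "interaction terms between quarters and randomization arm will be included to assess whether effects remain constant, intensify, or diminish over time", and gives the window as quarters 1 through 6. It does not say whether quarter is linear or categorical. It sets no size of loss that would count as waning and no criterion for calling an effect constant.

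The stated power, "80-85% statistical power to detect a difference between the arms for each of the outcomes of interest", concerns the main arm comparison in quarters 1-4. No power is given for the interaction.

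The Procedures section gives the enhanced package to 11 standard clusters in quarter 5 and to the other 11 in quarter 6.

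**The concern.** Constancy is the null hypothesis of an interaction test. A non-significant result supports it only if the test would probably have detected a loss that matters, and the plan neither names such a loss nor shows that power.

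The quarters 1-6 window adds a second problem. The interaction is with randomization arm, yet by quarter 6 both arms have the package. The arm contrast must then shrink even if the enhanced clusters keep all their gains.

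Scalability and sustainability are the plan's reasons for the blended format, and Aim 3 extends its model to the national program for up to five years. A wrong statement in either direction about whether gains last would bear on that use.

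**Working it through.** **Inputs.** From the Aim 2 section:
- 11 enhanced and 22 standard clusters over four quarters ("44 observations in the enhanced arm and 88 observations in the standard arm");
- "approximately 407 total potential indexes per facility per quarter";
- rates, random intercept variance (RIV) and scale from the primary power table, for example "0.3100 0.2113 1.47 126 86 0.0981 0.0854 85" for total indexes;
- "Nominal type I error rate of $\alpha=0.05$ is used throughout", with no adjustment for multiple endpoints.

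Assumed, because not given: a two-sided test, the same mean of 407 in every cluster, the full planned effect in quarter 1, and no baseline adjustment.

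**Step 1: reproduce the stated power.** Let L = ln(rate ratio) and v = 1/mean count + scale.

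SE² = (RIV + v_E/4)/11 + (RIV + v_S/4)/22; power = Φ(L/SE − 1.96).

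Total indexes: L = ln(0.3100/0.2113) = 0.383, v_E = 1/126.2 + 0.0854 = 0.0933, v_S = 1/86.0 + 0.0854 = 0.0970. SE = 0.129, L/SE = 2.975, power 84.5% (stated 85%). The table below gives all five. Only self-test kits differ by much (86% against 82%). A simulation of 500 trials per endpoint, fitting the negative binomial mixed model, gave 83.4, 79.6, 83.4, 83.4 and 83.6%, all within 2 points of the stated figures.

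**Step 2: total loss within quarters 1-4.** Let the log rate ratio fall linearly: L, 2L/3, L/3, 0. The random intercept cancels in within-cluster contrasts. In quarter q the arm difference has variance V_q = (1/μ_Eq + scale)/11 + (1/μ_S + scale)/22. With quarter scores c = −1.5, −0.5, 0.5, 1.5 (Σc² = 5), the size of the interaction slope is L/3 and its SE is √(Σc²V_q)/5.

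Total indexes: slope 0.128, SE 0.0511, z = 2.50. Miss rate = 1 − Φ(2.50 − 1.96) = 29.5%. The 3-df figure comes from the noncentral chi-square distribution for the three quarter differences.

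**Step 3: full maintenance over quarters 1-6, arm as randomized.** If crossed-over clusters gain the full effect at once, the arm contrast is L in quarters 1-4, L/2 in quarter 5 and 0 in quarter 6. With scores −2.5 to 2.5 (Σc² = 17.5), Σc·d = −3.25L. Total indexes: 3.25 × 0.383 = 1.246; SE = √(Σc²V_q) = 0.474; z = 2.63. Probability of a significant decline = Φ(2.63 − 1.96) = 75%, although nothing has waned.

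| Endpoint | Main power, closed form (stated) | Miss, 1 df, Q1-4 | Miss, 3 df, Q1-4 | False decline, 1-df trend, Q1-6 |
|---|---|---|---|---|
| Indexes | 84.5% (85%) | 29.5% | 46% | 75% |
| Contacts elicited | 81.1% (81%) | 48% | 64% | 55% |
| Self-test kits | 86.3% (82%) | 79% | 86% | 22% |
| Contacts tested | 84.8% (85%) | 28% | 45% | 77% |
| HIV-positive contacts | 83.7% (82%) | 50% | 65% | 60% |

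Simulation of the 1-df column gave 27, 50, 78, 29 and 51%.

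**Sensitivity.** If the whole loss comes only in quarter 4, the 1-df test misses it in 37-83% of trials. If it comes from quarter 3 on, 14-73%. If the log rate ratio falls linearly to half, 75-92%. Over quarters 1-6 with crossover, linear total loss by quarter 4 is missed in only about 0-29% (trend) or 0-54% (joint test), because crossover itself pushes the contrast down.

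**Precision of a late/early ratio.** The log ratio of the Q3-4 to the Q1-2 rate ratio has variance v_E/11 + v_S/22. Its 95% CI runs from the estimate divided by, to the estimate multiplied by, 1.25, 1.38, 2.76, 1.50 and 1.69 for the five endpoints in order. If the effect is truly constant, the expected lower limits are about 0.80, 0.72, 0.36, 0.67 and 0.59.

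**The case against.** Four points can be made for the plan.

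1. A reader might infer that the plan will label any non-significant interaction as constant. It does not say so. The wording poses a question, and rate ratios with 95% CIs are the stated style for the main analyses. This stands: the fault is a missing criterion, not a written misreading. A claim that a package with no effect would be declared constant in about 95% of trials depends wholly on the unwritten rule, and the main rate ratio would expose such a package anyway. Interval reporting is not, however, extended to the interaction or to quarter-specific effects.

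2. A reader might take 28-79% as the miss rate of the planned test. It is not. The plan's window is quarters 1-6, and under the crossover assumption above a loss is missed less often there. This also stands, but it does not rescue the test, which would report a decline in many trials where none occurred.

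3. The interaction is not the only evidence on maintenance. The plan also compares period A with period C, tests fidelity over time by arm, and holds quarter 4 focus groups. Nor is it one of the five powered comparisons. This limits the weight of the point. But the A-versus-C comparison is exploratory and has no margin either, and the fidelity test and focus groups do not measure uptake.

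4. The figures depend on decay shape and on how quarter is coded. True; the plan fixes neither, so each figure must be quoted with its conditions.

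**Conclusion.** The point holds in this form. The planned interaction analysis has no criterion and no shown power, and cannot support a conclusion that uptake effects remained constant. In quarters 1-4, linear loss of the whole planned effect would go undetected in about 28-79% of trials (1 df) or 45-86% (3 df). Over the stated quarters 1-6, analyzed by randomized arm, a fully maintained effect would show as a significant decline in about 22-77%. The first range rests on equal cluster means of 407, a two-sided 5% test and linear decay; unequal cluster sizes would lower power for the low-count endpoints. The second also rests on an immediate full effect after crossover, and a slower or smaller gain would reduce it. The primary quarters 1-4 arm comparison is not affected.

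**What to change.** In the Aim 2 Analyses paragraph:

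- Restrict the randomized maintenance contrast to quarters 1-4. If quarters 5-6 are used, code actual exposure rather than randomized arm.
- From the same negative binomial mixed model, report for each endpoint the arm rate ratio for Q1-2 and for Q3-4 (or each quarter) and the late/early ratio of rate ratios, all with 95% CIs.
- State that a non-significant interaction is not evidence that effects remained constant.
- Claim that the size of the effect was maintained only if the CI of the late/early ratio excludes a loss stated in advance. Claim that it diminished or intensified only if that CI lies wholly below or above 1. Otherwise report inconclusive.
- Describe a Q3-4 lower limit above 1 as an effect still present in Q3-4, not as maintenance. Used as a maintenance rule, it would pass an effect whose log rate ratio had fallen linearly to half by quarter 4 in about 24-36% of trials, while the late/early CI would show a decline in only 7-21%.

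Apply the same wording to the effectiveness part of maintenance in the Evaluation framework section.

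Cost: protocol wording and a few contrasts from a model already planned; no new data. Several endpoints will probably be inconclusive, self-test kits above all. For kits, even complete disappearance from a late/early ratio of 1 to 1/2.20 = 0.45 lies inside the expected interval, whose lower limit is about 0.36.
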